8.6 Definition of a Serious Adverse Event (SAE)

An SAE is any adverse drug experience occurring at any dose that results in any of the following outcomes:

- death,
- a life-threatening event (at risk of death at the time of the event),
- requires inpatient hospitalization or prolongation of existing hospitalization,
- a persistent or significant disability/incapacity, or
- a congenital anomaly/birth defect in the offspring of a subject.

Important medical events that may not result in death, be life-threatening, or require hospitalization may be considered a serious adverse drug event when, based upon appropriate medical judgment, they may jeopardize the subject and may require medical or surgical intervention to prevent one of the outcomes listed in this definition.

A distinction should be drawn between serious and severe AEs. A severe AE is a major event of its type. A severe AE does not necessarily need to be considered serious. For example, nausea which persists for several hours may be considered severe nausea, but would not be an SAE. On the other hand, a stroke that results in only a limited degree of disability may be considered a mild stroke, but would be an SAE.

8.6.1 Relationship of SAE to Study Intervention

The relationship of each SAE to the study intervention will be characterized using one of the following terms in accordance with CHOP IRB Guidelines: definitely, probably, possibly, unlikely, or unrelated.

8.7 IRB/IEC Notification of SAEs and Other Unanticipated Problems

The Investigator will promptly notify the IRB of all on-site unanticipated, serious Adverse Events that are related to the research activity. Other unanticipated problems related to the research involving risk to subjects or others will also be reported promptly. Written reports will be filed using the eIRB system and in accordance with the timeline below. External SAEs that are both unexpected and related to the study intervention will be reported promptly after the investigator receives the report.

| Type of Unanticipated Problem | Initial Notification (Phone, Email, Fax) | Written Report |
|--|---|---|
| Internal (on-site) SAEs Death or Life Threatening | 24 hours | Within 2 calendar days |
| Internal (on-site) SAEs All other SAEs | 7 days | Within 7 business days |
| Unanticipated Problems Related to Research | 7 days | Within 7 business days |
| All other AEs | N/A | Brief summary of important AEs may be reported at time of continuing review |

8.7.1 Follow-up report

If an SAE has not resolved at the time of the initial report and new information arises that changes the investigator's assessment of the event, a follow-up report including all relevant new or reassessed information (e.g., concomitant medication, medical history) will be submitted to the IRB. The investigator is responsible for ensuring that all SAE are followed until either resolved or stable.

8.8 Investigator Reporting of a Serious Adverse Event to Sponsor

Reporting will be consistent with regulatory requirements.

8.9 Medical Emergencies

As this study involves inpatient hospital admissions, any medical emergencies will be handled per standard operating procedure.

9 STUDY ADMINISTRATION

As this is an open-label, pilot clinical trial, there will be no control or experimental cohort assignments and no blinding.

9.1 Data Collection and Management

9.1.1 Confidentiality of Data

All information that is collected for this research protocol will be kept confidential. All subjects will be assigned a unique study identification number (study ID). This study ID will be used on all case report forms (CRFs). The investigators will maintain a master list

separate from data forms that have only a study number. Only password-protected files will be used to store the data.

9.1.2 Security

A copy of the password-protected file will be kept in the investigator's office computer, with the original in one of the Hospital's secure servers.

9.1.3 Anonymization, de-identification or destruction

All data will be maintained the longer of either (A) 6 years after completion of the study or (B) 2 years after the last marketing approval or if no application is filed or approved, 2 years after the FDA is notified of discontinued application. The investigator maintains a file drawer specifically for such archives, each folder labeled "Destroy by....," with the earliest dates at the front. The CHOP PI will monitor and review the study progress and the accuracy and security of the emerging data.

9.2 Confidentiality

All data and records generated during this study will be kept confidential in accordance with Institutional policies and HIPAA on subject privacy. The Investigators and other site personnel will not use such data and records for any purpose other than conducting the study. Safeguards are described under Data Collection and Management.

No identifiable data will be used for future study without first obtaining IRB approval. The investigator will obtain a data use agreement between the provider (the PI) of the data and any recipient researchers (including others at CHOP) before sharing a limited dataset (PHI limited to dates and zip codes).

9.3 Regulatory and Ethical Considerations

This study is to be conducted according to US and international standards of Good Clinical Practice (FDA Title 21 part 312 and International Conference on Harmonization guidelines), applicable government regulations and Institutional research policies and procedures. Investigators will follow ICH guidelines as they pertain to this study.

This protocol and any amendments will be submitted to a properly constituted Institutional Review Board (IRB), in agreement with local legal prescriptions, for formal approval of the study conduct. The decision of the IRB concerning the conduct of the study will be made in writing to the investigator and a copy of this decision will be provided to the sponsor before commencement of this study.

All subjects for this study will be provided a consent form describing this study and providing sufficient information for subjects to make an informed decision about their participation in this study. This consent form will be submitted with the protocol for review and approval by the IRB for the study. The formal consent of a subject, using the EC/IRB-approved consent form, will be obtained before that subject is submitted to any study procedure. This consent form will be signed by the subject or legally acceptable surrogate, and the investigator-designated research professional obtaining the consent.

9.3.1 Data and Safety Monitoring Plan

The principal investigator will monitor study progress, ensure subject safety, and the accuracy and security of the data at CHOP, and will report any adverse events in accordance with the FDA regulations and IRB policies.

Prior to trial initiation, pre-trial visit will be completed by the Office of Research Compliance (ORC) to confirm trial readiness. After the first subject enrolls and completes the first investigational admission, the PI will contact ORC to arrange a monitoring visit. Thereafter, ORC will monitor the study annually. Monitoring activities will be guided by ICH E6 section 5.18. Interim monitoring activities will include a review of regulatory files as well as a percentage of enrolled subject records, source documents, applicable informed consent forms, and case report forms. The percentage of subject data review may be amended throughout the course of the study based on an ongoing risk assessment. A tapered approach to monitoring may be employed if conduct and documentation of the study reaches a level of reliability that would permit valid conclusions based upon a sampling of data.

During the experiment, CGMS data will be collected in various ways. CGMS data, calibration data, insulin dosing data, and glucagon dosing data will be automatically stored in the bionic pancreas device (from which it will be downloaded) and wirelessly streamed to the cloud where it will be stored to provide redundancy in data storage and mitigate the risk of data loss. During the control phase, CGMS data will be downloaded at intervals. All data will be combined in a single database that will be compared against the primary data files for integrity. The computer database will be backed up at least monthly and the backup media stored in a secure location.

The PI and the Bionic Pancreas team will be involved in education of the staff prior to the start of the protocol and will communicate with staff as required during the performance of the trial. Study staff will be encouraged to raise any concerns they may have or problems they have identified at any time. The PI will decide a course of corrective action, and resolution or progress will be assessed no later than the next meeting.

A numeric code will be substituted for the subjects personal identifying information in the study database, which will be password protected. The key linking the medical record number of the subject with the numeric code, along with case report forms, and all information that is personally identifiable, will be kept in a locked filing cabinet in an investigator's locked office. All electronic records will be kept in a password protected computer database. All printed computer data will be disposed of confidentially when no longer needed. Only the study staff will have access to the study database. Subjects may not withdraw from the de-identified database, but they may elect to have the key linking their medical record to the de-identified database destroyed.

Data/CRFs will be stored in OnCore Clinical Trials Management System, a CHOP Research IS secured electronic data capture system. OnCore Clinical Trials Management System is a secure electronic data capture system with access controls and a data backup plan. The system is password protected. Only study team members will have access to subject data and case report forms stored in OnCore. Access to the system is monitored and logged for review if needed.

The study data will be shared with collaborators from the Bionic Pancreas team, but only in a form in which all personally identifiable information has been removed (e.g. combined database including blood glucose values, record of insulin and glucagon delivered by the device, and blood insulin and glucagon levels). Shared data will be in the form of a database in which only a number identifies subjects.

Subjects may not withdraw their data, as it will be stored in non-personally identifiable form.

9.3.2 Safety Monitoring

An Independent Safety Officer with expertise in Diabetes and Clinical Trials will oversee the conduct of the study and review its results after 3 subjects have completed the study and again when all subjects complete the study. Additionally, the Safety Officer will be informed in the event of any severe or unexpected adverse events. The Safety Officer will be informed if there are any changes to the study protocol that could significantly impact the safety or scientific validity of the study. Safety and efficacy data will also be reported to the FDA in compliance with applicable regulations.

The study will stop and discussion with the Safety Officer will be required to restart it if more than one subject experiences the same adverse event due to malfunction of the bionic pancreas system:

- Diabetic ketoacidosis requiring hospitalization
- Seizure or unconsciousness associated with hypoglycemia
- Persistent nausea and vomiting thought to be related to glucagon dosing.

If more than 3 subjects must be withdrawn from the study for these reasons, the study will stop and discussion with the Safety Officer will be required to restart it. All serious and unexpected events will be reported to the Safety Officer within 72 hours.

Note that subjects may discontinue participation at any time and subjects may be removed from the trial for other reasons, for instance failure to comply with study procedures or inter-current illness that is unrelated to the bionic pancreas but that precludes safe participation. Discontinuation of participation for these reasons will not contribute to a decision to discontinue the trial.

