| Study Design | This will be an open-label, pilot clinical trial to assess efficacy and safety of the bihormonal bionic pancreas in children and adults with HI who have developed post-pancreatectomy diabetes. Subjects will be studied during two research inpatient admissions at the CHOP HI Center. The order of the interventions will be randomized. |
| Subject Population | 
Abbreviated Inclusion Criteria
 
 1. Individuals 6 years to 30 years of age. 2. Diagnosis of hyperinsulinism. 3. Previous pancreatectomy. 4. Diagnosis of diabetes. 5. Treatment with subcutaneous insulin by pump at the time of recruitment. 
Abbreviated Exclusion Criteria
 
 1. Evidence of a medical condition that might alter results or compromise the interpretation of results, including active infection, kidney failure, severe liver dysfunction, severe respiratory or cardiac failure. 2. Evidence of severe hematologic abnormality including severe anemia and/or thrombocytopenia. |
| Number of Subjects | 12 subjects enrolled to produce 10 evaluable subjects |
| Study Duration | Each subject's participation will last approximately 8 days (screening visit and two, 4-day inpatient admissions). The entire study is expected to last one year. |
| Study Phases | 
 • Screening: medical records will be reviewed to determine eligibility. Medical history, physical examination, CBC, CMP, and HbA1c will be obtained during this visit after informed consent. • The order of admissions will be determined using a randomized, cross-over design and will occur at least 1 week apart. • Standard Care Admission: A 4-day inpatient admission in which subjects will continue their home insulin regimen. The first day will be a run-in period. The last 3 days involve collection of plasma glucose data for analysis (CGMS and fingerstick). • Bihormonal Bionic Pancreas Admission: A 4-day inpatient admission in which subjects will wear the bihormonal pancreas. |

| | |
|--|---|
| | 
The bihormonal pancreas will be placed upon admission and there will be 1 day of run-in followed by 3 days of data collection for comparison with the data obtained from the standard of care during the control admission. Following this, the patient will transition back to their home regimen and discharged home.
 |

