3.1.1 Screening Phase

Potential subjects will be screened using the protocol inclusion and exclusion criteria. Individuals with HI and post-pancreatectomy diabetes will be recruited from the CHOP Congenital Hyperinsulinism Center.

Parental/guardian permission (informed consent) and, if applicable, child assent, will be obtained prior to any study related procedures being performed.

Medical records will be reviewed to determine eligibility. Medical history, physical examination, CBC, CMP, and hemoglobin A1c will be obtained during this visit after informed consent. Blood samples will be drawn to confirm eligibility based on clinical laboratory parameters. Females ≥ 11 years of age will have a urine pregnancy test.

The order of admissions will be determined based upon a randomized, crossover design with at least one week between admissions.

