3.3.2 Total Number of Subjects Projected

It is expected that approximately 12 subjects will be enrolled to produce 10 evaluable subjects.

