4.3 Experimental Procedures and Data Collection

4.3.1 Screening Visit

- After informed consent is obtained, all subjects will have a screening visit to confirm eligibility.
 - The subject will be interviewed and the case report form will be completed by study staff to establish whether the subject is eligible to continue with the screening according to inclusion/exclusion criteria, in the event the medical record review provided outdated data.
 - Demographic/medical history data to be recorded:
 - Age
 - Sex
 - Race and ethnicity
-

- Date of HI diagnosis
- Date of pancreatectomy and percentage removed
- Date of diabetes diagnosis/insulin initiation
- Medical, surgical, and social history, allergies, and review of systems relevant to inclusion and exclusion criteria
- Medications (prescription and non-prescription)
- Duration of insulin pump use
- Type of insulin used in pump
- Average total daily dose of insulin in the last 30 days (from pump history, as available – for comparison with insulin dosing during the standard care and bionic pancreas arms of the study)
- Usage of CGMS, if any (type of CGMS, days per month worn, usage of data, whether insulin is dosed based on CGMS alone, alarm settings)
- Physical examination
- Vital Signs: height, weight, temperature, blood pressure, heart rate, respiratory rate
- Pregnancy test (for female subjects 11 years and older)
- Safety laboratory tests: CBC, CMP, hemoglobin A1c
- Once all the laboratory results have been returned, a study physician will review the case report form to determine subject eligibility to continue in the study. If subjects are not eligible to continue in the study, the results of abnormal tests will be reported to the subjects.
- Subjects who have been screened and are eligible can participate without having to be rescreened for a period of one year. The study staff should obtain verbal confirmation that there have been no health events that would make them ineligible if the interval between screening and participation is longer than 3 months.
- Upon confirmation of eligibility and participant’s willingness to continue, subjects will be assigned to an order of admissions based upon a randomized, crossover design. There will be a minimum of 1 week time between admissions.
- Pediatric subjects will be required to have a parent or guardian accompanying them during the inpatient admissions.

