4.9 Rescue Medication Administration

4.9.1 Response to Hypoglycemia

- BG will be checked for any symptoms of hypoglycemia.
- Hypoglycemia will be treated according to standard of practice according to the “rule of 15s”: take 15 grams of rapid acting carbohydrate and recheck in 15 minutes, then repeat as needed. For severe episodes of hypoglycemia that are not responsive to carbohydrate ingestion or if the subject cannot drink/eat, 1 mg of glucagon subcutaneously or intramuscularly will be administered as necessary.
- During the bionic pancreas admission the glucagon infusion site and the bionic pancreas will be checked for normal operation any time hypoglycemia occurs. If there is any suspicion of glucagon infusion set malfunction, the site will be replaced.
- If a subject experiences a seizure or unconsciousness associated with hypoglycemia, his or her participation in the study will be discontinued.

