4.12 Subject Completion/Withdrawal

Subjects may withdraw from the study at any time without prejudice to their care. They may also be discontinued from the study at the discretion of the Investigator for lack of adherence to study treatment or visit schedules, AEs, or SAEs. The Investigator may also withdraw subjects who violate the study plan, or to protect the subject for reasons of safety or for administrative reasons. It will be documented whether or not each subject completes the clinical study. If the Investigator becomes aware of any serious, related adverse events after the subject completes or withdraws from the study, they will be recorded in the source documents and on the CRF. When a subject discontinues/withdraws prior to study completion, the study staff reserves the right to analyze data from studies completed prior to withdrawal.

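### The first scheduled Safety Officer review counts study completers, not device exposures, so more than 3 subjects may have used the device before it takes place

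*Combined protocol and SAP*

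**What the plan says.** Section 9.3.2 has an Independent Safety Officer oversee the study and "review its results after 3 subjects have completed the study and again when all subjects complete the study". No other Safety Officer review is scheduled.

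Completing the study means finishing both admissions: section 3.3.1 describes participation as screening plus the two 4-day stays. Section 4.12 keeps completion apart from withdrawal ("It will be documented whether or not each subject completes the clinical study"). Under 4.9.1, a subject with a hypoglycemic seizure or unconsciousness is taken off study ("his or her participation in the study will be discontinued"). Sections 4.9.2 and 4.9.3 say the same for diabetic ketoacidosis and for persistent glucagon-related nausea and vomiting.

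Order is randomised, and the interval between admissions has a lower bound only: "There will be a minimum of 1 week time between admissions" (4.3.1; likewise 3.1.1). Section 3.3.2 expects that "approximately 12 subjects will be enrolled to produce 10 evaluable subjects". On timing, the Synopsis says "The entire study is expected to last one year". Nothing staggers subjects or holds enrolment for the review.

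Section 9.3.2 also has safeguards that do not depend on completion. The Safety Officer is told of severe or unexpected adverse events, and receives serious and unexpected ones within 72 hours. The study stops, pending discussion with the Safety Officer, if more than one subject has the same listed event through device malfunction, or if more than 3 subjects are withdrawn for the listed reasons. Section 6.7 adds ongoing examination of safety data, without naming who does it.

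**The concern.** All the human experience cited for the device is in type 1 diabetes, and section 1.4 explains why this population differs: residual dysregulated insulin secretion together with glucagon deficiency. An early independent look at the first few device users is therefore worth having.

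The trigger measures something else. A subject who comes off study because of the device never counts towards the 3, so the outcomes that most call for a review push it later. A device-first subject adds to exposure at once but to the count only after a second admission that has no latest date. The closing review comes too late to affect any participant.

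At stake are the signals that fall below the notice thresholds. Section 6.3 lists carbohydrate interventions, glucagon total daily dose, device downtime and nausea score as safety endpoints. Section 8.5.1 treats hypoglycemia and hyperglycemia as expected and reports them only above set thresholds. The text gives the Safety Officer no defined route to this accumulating information except a scheduled review.

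**Working it through.** The trigger of 3 is a rule and not a derived figure, so there is nothing of the plan's to reproduce. The question is how many subjects have started the device when the third subject completes.

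**Inputs.** From the documents: 12 enrolled and 10 evaluable (3.3.2), 4-day admissions (3.3.1), a gap of at least 1 week (4.3.1), and one year for the study (Synopsis). Assumed: 6 subjects per order, the entry pattern, any gap longer than 1 week, and the timing and cause of losses. None of these is stated.

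**1. Overlap caused by the crossover, no losses.** Entry times are uniform over the entry period. For gap g weeks, a subject entering on day s has the second admission on day s + 4 + 7g and completes 4 days later. The device starts on day s (device first) or s + 4 + 7g (standard care first). Mean number with device start on or before the third completion, by simulation:

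| Entry period | g = 1 | g = 12 | g = 26 |
|---|---|---|---|
| 52 weeks | 3.3 | 4.6 | 6.2 |
| 26 weeks | 3.6 | 6.2 | 7.6 |

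With 52-week entry, the chance that more than 3 have been exposed is 28% at a 1-week gap and 50% at 4 weeks. If entry is evenly spaced over the year instead, the means are 3.0, 4.5 and 6.0 for gaps of 1, 13 and 26 weeks.

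**2. Losses after device use, one subject at a time.** If each subject is lost with probability q after using the device, the expected number exposed at the third completion is 3/(1 − q), and P(more than 3) = 1 − (1 − q)³. The plan implies q = 2/12 overall, with causes not given. If every loss follows device use, 3/(10/12) = 3.6 and 1 − (10/12)³ = 0.42.

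**3. Limits.** If all losses are for the listed reasons, the fourth such withdrawal stops the study, so one-at-a-time exposure before a review or a stop is at most 2 completers + 4 withdrawals = 6. With no losses, all first admissions done before any second, and second admissions run singly, the most exposed at the third completion is 6 device-first + 3 standard-first = 9.

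**4. Trigger tied to the device admission.** In the setting of step 1 (52-week entry, 1-week gap), counting the third finished device admission gives a mean of about 3.1. The excess over 3 is a device admission already under way. This figure hardly moves with the gap, because each device admission counts as soon as it ends.

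**The case against.** The strongest reply is that the effect is small on the plan's own terms and that the serious cases are covered elsewhere. Much of this stands.

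A reader might infer that many more than 3 subjects, or even all 12, would be exposed before anyone independent looks. The documents do not support that. At the only gap they state, with entry over a year, the mean is about 3.3. The larger figures need gaps or an entry pace that the text permits but does not plan. No cap below 12 is written down, but reaching 12 would take many simultaneous device admissions or many withdrawals.

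A reader might also infer that severe toxicity would go unseen. It should not: the three kinds of event that end participation under 4.9 are those named in the stop rules, and severe or unexpected events are notified individually. There are limits. The first stop rule requires malfunction, and adverse-event withdrawals for other reasons fall outside both rules. Section 9.3.2 also says severe or unexpected in one place and serious and unexpected in another, while 8.6 separates severe from serious. Those statements must be reconciled.

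Nor does anything exclude discontinued subjects from what is reviewed. The Safety Officer reviews the study's results, and sections 6.5 and 6.5.3 define safety data broadly. The problem is when the review happens; its content needs only to be made explicit.

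Finally, counting completers has a rationale, since each supplies a within-subject comparison with standard care. That is a real benefit, but section 6.5 itself defines the population for safety and tolerability by device placement, not by completion.

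**Conclusion.** The concern holds in a limited form. The one scheduled review that can help later subjects is keyed to completing both admissions, so device-related discontinuation and device-first ordering can both delay it. The expected excess is small at the stated minimum gap (about 3.3 exposed, against about 3.1 under a device-based trigger) and grows to about 4.6 to 6.2 if gaps of 12 to 26 weeks are assumed. These means rest on uniform entry over a year, 6 subjects per order and no losses. Losses after device use would add to them.

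The gap that remains concerns signals below the notice thresholds; the severe events are largely handled by the notices and stop rules. The change is cheap enough to be worth making.

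**What to change.** In 9.3.2, set the first review to take place after the third subject has completed or been discontinued from a Bihormonal Bionic Pancreas Admission, in either order. Keep the number 3 and the end-of-study review. Section 9.3.1 already ties its compliance visit to an admission; that visit is made by a different body and is not a safety review, but it shows that such a trigger is workable.

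State that the review covers all subjects who had the device placed (the All Subjects as Treated population of 6.5), including the 6.3 safety endpoints, with glucagon total daily dose set beside the expected figure in 7.1 (below 1.5 mg daily). Insulin cannot be treated in the same way: 7.1 gives limits for single insulin doses but no expected daily total.

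The cost is a sentence or two, with no added visits or staff. The downside is that fewer paired standard care admissions may be available at that review. The change does not hold enrolment, so a device admission under way could still overlap with it.
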